## LIST OF ABBREVIATIONS

Abbreviation	Definition
ADaM	Analysis Data Model
AE	Adverse event
ATC	Anatomical therapeutic chemical
AUC	Area under curve
BID	Twice daily
BLQ	Below limit of quantification
BMI	Body mass index
CDISC	Clinical Data Interchange Standards Consortium
CFU	Colony-Forming Unit
COVID-19	Coronavirus disease 2019
CRF	Case report form
CRISPR	Clustered Regularly Interspersed Short Palindromic Repeats
crPhages	CRISPR-enhanced bacteriophage
CSR	Clinical Study Report
DAIDS	Division of AIDS (Acquired immunodeficiency syndrome)
DSMC	Data Safety Monitoring Committee
E. coli	Escherichia coli
ECG	Electrocardiogram
EOS	End of study
EOT	End of treatment
FIH	First in human
GM	Geometric mean
IgA	Immunoglobulin A
IgE	Immunoglobulin E
IgG	Immunoglobulin G
IgM	Immunoglobulin M
IMP	Investigational Medicinal Product
ITT	Intent-to-Treat
IVRS	Interactive voice/web-based response system
MedDRA	Medical Dictionary for Regulatory Activities
PD	Pharmacodynamics
PK	Pharmacokinetics
PFU	Plaque-forming unit
RBC	Red blood cell
SAE	Serious adverse event
SAP	Statistical Analysis Plan
SD	Standard deviation
SDTM	Study Data Tabulation Model
SoA	Schedule of Assessments
TEAE	Treatment-emergent adverse event
TESAE	Treatment-emergent serious adverse event
TFL	Table, figure, listing
USP	United States Pharmacopeia
UTI	Urinary tract infection
WBC	White blood cell
WHO	World Health Organization

## 1 INTRODUCTION

The purpose of this Statistical Analysis Plan (SAP) is to provide a description of the statistical methods to be implemented for the analysis of data from the study with protocol number LBx-1001. The SAP will be finalized prior to database lock. Any deviations from the SAP after database lock will be documented in the final Clinical Study Report (CSR).

## 2 STUDY OVERVIEW

### 2.1 Study Objectives

#### 2.1.1 *Primary Objective*

To evaluate the safety, tolerability, and pharmacokinetics (PK) of LBP-EC01 in patients  $\geq 18$  yrs of age with lower urinary tract colonization caused by *E. coli*.

#### 2.1.2 *Secondary Objectives*

To evaluate the pharmacodynamics (PD) of LBP-EC01.

#### 2.1.3 *Exploratory Objectives*

To explore the influence of LBP-EC01 on the urinary tract microbiota.

### 2.2 Study Design

#### 2.2.1 *Overview*

This is a Phase 1b FIH study to assess safety, tolerability, PK, and PD of LBP-EC01 in patients who have significant colonization of the urinary tract by *E. coli*. It is a multi-center randomized, double-blind study in patients with indwelling urinary catheters, or who require intermittent urinary catheterization and/or patients with asymptomatic bacteriuria caused by *E. coli*.

No formal hypothesis will be tested. Thirty-six patients will be randomized 2:1 to receive either LBP-EC01 (at approximately  $1.5 \times 10^7$  -  $1.5 \times 10^{13}$  PFU/vial - the maximum feasible dose based on manufacturing process) or inert placebo given twice daily for 7 days by intravesical catheter. A new catheter will be installed at the beginning of the study and will be replaced at the discretion of the investigator. The study will be conducted in 7 sites in the US. Study duration for patients will be up to 56 days, which includes up to 21 days for screening, 7 days of Investigational Medicinal Product (IMP) treatment, a Day 14 assessment (14 days after first dose), a Day 28 assessment (28 days after first dose), and an End of Study (EOS) assessment (35 days after first dose). Patients will be in the clinic or hospital the evening prior to receiving the first dose of treatment and throughout the 7 days of treatment.

The study will consist of a Screening Period of up to 21 days. On Day -1 patients will either be hospitalized or in a facility that can provide proper administration of study drug and then randomized to LBP-EC01 or placebo. The entire 7-day Treatment Period in which patients will receive 13 doses of IMP will be conducted with the patient in the clinic/hospital. In circumstances where the patient may not be able to be in clinic/hospital for the full 7 days of treatment, upon consultation between the treating physician and the study Medical Monitor, patients may be considered to be treated and monitored in clinic/hospital for Days 1-3 and then may be allowed to come back to the clinic/hospital for the PM dose on Day 3 and the remaining treatment from Days 4-7. The end of treatment (EOT) will be after the 13th dose on Day 7, after

which the patient may be released from the clinic/hospital. The patient will return on Day 14 ( $\pm 3$  days) for the Day 14 Visit, and on Day 28 ( $\pm 3$  days) for the Day 28 Visit. AE data will be collected throughout the study, including Day 28 through Day 35. At Day 35, the patient will be contacted by telephone to assess any AEs or lab abnormalities since the Day 28 Visit. At the discretion of the investigator, the patient may be asked to return to the clinic/hospital for a Day 35 Visit ( $\pm 3$  days). Day 35 is the end of study. Assessments will be conducted as described in Table 1 and Table 2 of the Protocol.

Safety will be assessed throughout the study. Spleen evaluations will include ultrasound assessments for splenomegaly at Day -6 to -1, Day 3, and Day 7 and clinical examinations to assess for splenomegaly will be performed at all visits. In addition, attention will be focused on identifying any progression of a urinary colonization to an active infection, including the signs and symptoms of local vesicular reactions (e.g., bladder pain, hematuria). Symptoms of active infection will be solicited during daily observations throughout the 7 days of treatment and until the end of study. Symptoms of note in this population include dysuria, urinary frequency, urinary urgency, suprapubic discomfort and flank pain in addition to non-specific symptoms of urinary leakage, change in voiding habits, worsening muscle spasm, increasing autonomic dysreflexia, sweating, malaise, and fever or hypothermia. Urine microscopy and culture will be assessed frequently during the study (see Table 2 of the Protocol).

#### 2.2.2 *Randomization and Blinding*

Study patients will be randomly assigned to LBP-EC01 or placebo treatment groups in a 2:1 ratio using IVRS.

This is a double-blind study. Blinding to study treatment allocation will be achieved through use of matching placebo solution and administration sets. Neither the patient, nor the Investigator, nor Medpace/Sponsor will be aware of the treatment allocation. Key pharmacy staff involved in the preparation of the IMP or placebo will need to be unblinded.

In the event of an emergency, the treatment code for an individual patient will be readily available to the Investigator and Sponsor/Medpace through the IVRS. If unblinding is necessary for patient management (in the case of an SAE), the Investigator will be able to break the treatment code by contacting the IVRS. Treatment codes should not be broken except in emergency situations. If the Investigator wishes to know the identity of the IMP for any other reason, he or she should contact the Medical Monitor directly. The Investigator should document and provide an explanation for any premature unblinding (e.g., accidental unblinding, unblinding due to an SAE).

As per Health Authority reporting requirements, the Sponsor/Medpace will break the treatment code for all unexpected SAEs (see Section 9.3 of the Protocol) that are considered by the Investigator to be related to IMP.

Whenever disclosure of the identity of the IMP is necessary, adequate procedures will be in place to ensure integrity of the data. Any unblinding, at the investigating site end, will be documented in the study report with date, reason for identifying the drug and the name of all the person(s) who required unblinding.

#### 2.2.3 *Study Drug*

LBP-EC01 is a clear to opalescent, colorless to slightly yellow, aqueous solution. LBP-EC01 is a mixture of 3 crPhages internally named as p0031-8, p00ex-2, p004k-5, which are derived from wild-type myoviridae phages that target *E. coli*. These phages have been engineered to contain

an identical CRISPR-Cas3 construct and have been combined in equal amounts at  $1 \times 10^6$  –  $1 \times 10^{12}$  PFU/mL (equivalent to approximately  $1.5 \times 10^7$  –  $1.5 \times 10^{13}$  PFU/vial). One vial of LBP-EC01 containing approximately 15 mL of solution will be steriley mixed with 45 mL of Lactated Ringer's solution (injection, USP) by the site pharmacy prior to each dose administered (details will be included in the pharmacy manual). LBP-EC01 and placebo solutions will be indistinguishable.

LBP-EC01 will be administered by bladder instillation via a newly placed urinary catheter BID at the maximum feasible dose, based on the manufacturing process (approximately  $1.5 \times 10^7$  –  $1.5 \times 10^{13}$  PFU/vial), totaling approximately 60 mL of solution via sterile catheter tipped syringe (details will be included in the pharmacy manual). The urinary catheter will be clamped and the solution left in situ for a minimum of 30 minutes (to a maximum of 40 minutes) following instillation and then it will be placed on free drainage (duration of clamp should be documented).

LBP-EC01 will be provided in a 20 mL vial containing approximately 15 mL of the crPhage cocktail. This vial will be brought to room temperature prior to mixing with 45 mL of Lactated Ringer's solution (injection, USP) under sterile conditions and placed into a sterile syringe with a catheter tip. Handling and mixing of the vials making up LBP-EC01 will be done by the unblinded study pharmacist (details are provided in the pharmacy manual). Placebo solution Lactated Ringer's solution (injection, USP) will be brought to room temperature and will also be prepared by the pharmacist under aseptic technique and placed into a sterile catheter tipped syringe. The unblinded pharmacist will use the IVRS system to determine the randomization allocation.

The mixed blinded solutions will be provided to the investigator/nursing staff for administration. If not used immediately, the IMP combined with Lactated Ringer's solution should be stored under refrigerated conditions and must be administered within 24 hours of preparation. Doses may be given at 8 AM within +/- a 2-hour window for the AM dose and 12 hours after the AM dose +/- a 3-hour window for the PM dose. The clinical site staff should consult with the Medical Monitor about any missed dose outside the allowable dosing window. Typically, these missed doses should be given and documented following standard procedure.

All patients will receive a total of 13 doses of drug product or placebo across 7 days of treatment (a single morning dose will be given on Day 7). All doses should be given using strict aseptic techniques and may be administered by clinic/hospital staff provided they have been given adequate training. Upon completion of the study, patients requiring subsequent catheterization should have their study catheter replaced. The catheter used in the study should be discarded per normal site policy.

#### 2.2.4 *Sample Size Determination*

36 patients were randomized in a 2:1 ratio to LBP-EC01 or placebo. This is a FIH study and the sample size should be sufficient to establish early safety and PK at a single dose level.

### 2.3 Study Endpoints

#### 2.3.1 *Primary Endpoints*

The primary endpoints involve summarizing the safety and tolerability of AEs and lab parameters, as well as the PK parameters of LBP-EC01. The PK parameters will be assessed as a combined set of all crPhages included in LBP-EC01 in both urine and blood.

The blood PK parameters will include the following assessments of LBP-EC01:

- Maximum concentration ( $C_{max}$ )
- Time to  $C_{max}$  ( $T_{max}$ )
- Area under the concentration versus time curve (AUC) from time 0 to the last measurable concentration ( $AUC_{0-t}$ )

Other PK variables may be calculated as appropriate for the observed data.

### 2.3.2 Secondary Endpoints

The secondary endpoints involve summarizing PD parameters of LBP-EC01. These include:

- Reduction in urinary *E. coli* burden at any of the following timepoints: Day 2, Day 3, Day 5, Day 7 (EOT), Day 14, and Day 28
- Time to 1 log reduction in urinary *E. coli* count
- Recurrence of *E. coli* colonization or incidence of infection based on clinical signs and symptoms
- Changes in IgA, IgE, IgG, and IgM levels

### 2.3.3 Exploratory Endpoints

The exploratory endpoints involve exploring the effects of LBP-EC01 on the urinary tract microbiota. These include:

- Urine culture and sensitivity (persistent, recurrent *E. coli*, new colonizing new infections will be documented)
- Evaluation of bacterial biomarkers (e.g., phage sensitivity/resistance, bacterial antibiotic resistance, bacterial metagenomic analysis)

### 2.3.4 Exploratory Analyses

Exploratory analyses will include:

- Differences between indwelling and intermittent urinary catheterization populations will be compared
- Any persisting microbiological isolates will be fully explored with bacteriophage host range, antibiotic resistance patterns and genetic sequencing of isolates

## 3 STATISTICAL METHODOLOGY

### 3.1 General Considerations

#### 3.1.1 *Definition of Baseline*

Baseline is defined as the last measurement prior to the first dose of study drug unless otherwise specified.

### *3.1.2 End of Treatment Definition*

The EOT is defined as the last date the patient received study drug, which is scheduled at Day 7.

### *3.1.3 End of Study Definition*

A patient is considered to have completed the study if he or she has completed all portions of the study including the last visit or the last scheduled procedure shown in the SoA (Table 1 of the Protocol).

The EOS is defined as the last date that patient safety data is collected (i.e., Day 35). Once patients have completed Day 28, they may resume their regular medications and have any new intermittent catheters re-established as directed by their physician.

### *3.1.4 Summary Statistics*

Categorical data will generally be summarized with counts and percentages of patients. The denominator used for the percentage calculation will be clearly defined. Continuous data will generally be summarized with descriptive statistics including n (number of non-missing values), mean, median, standard deviation, minimum, and maximum. Geometric mean (GM), and GM CV% will also be provided for PK parameters. The value of zero will be excluded from the calculation of GM and GM CV%.

### *3.1.5 Hypothesis Testing*

This is a Phase 1b study and primary outcomes are evaluation of safety, tolerability and PK. No formal hypothesis will be tested.

### *3.1.6 Handling of Dropouts and Missing Data*

Generally, missing data will be noted but not be imputed unless otherwise specified.

## 3.2 Analysis Populations

### *3.2.1 Safety Population*

The Safety Population is defined as all randomized patients who receive at least one dose of study drug. All safety data will be analyzed using the Safety Population.

### *3.2.2 Intent-to-Treat (ITT) Population*

The ITT Population is also defined as all randomized patients who receive at least one dose of study drug, thus the same as the Safety Population. The ITT Population will be the primary population for analysis of all secondary and exploratory endpoints except for those PD-related.

### *3.2.3 Evaluable Population*

The Evaluable Population is defined as all patients in the ITT Population who completed the study and who have been dosed according to protocol for the first 4 days of treatment and who have not been subject to a suspension of treatment or who have not missed more than one dose of study drug during the remainder of treatment (i.e., Days 5-7). Patients who show disease progression to active infection will be discontinued from treatment and treated for their symptoms and will be followed for safety. These patients will be included in the Evaluable Population as long as they have been dosed according to protocol for the first 4 days of

treatment. The Evaluable Population will be a secondary population for analysis of the non-PD secondary and exploratory endpoints.

A list of patients excluded from the Evaluable Population will be finalized prior to unblinding the randomized treatment assignments.

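### The Evaluable Population joins its two Days 5-7 conditions with *or*, so the one-missed-dose limit does not bind a patient whose treatment was not suspended

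*SAP*

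**What the plan says.** SAP section 3.2.3 builds the Evaluable Population from ITT patients who completed the study and "who have been dosed according to protocol for the first 4 days of treatment". It then adds two conditions on later dosing, covering Days 5-7, for patients "who have not been subject to a suspension of treatment or who have not missed more than one dose of study drug".

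A separate sentence covers infection: "Patients who show disease progression to active infection will be discontinued from treatment and treated for their symptoms". Of this group the section says: "These patients will be included in the Evaluable Population as long as they have been dosed according to protocol". That requirement again refers to Days 1-4.

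The set is secondary, for non-PD secondary and exploratory endpoints, and its exclusion list is to be finalized before unblinding. Section 3.6 summarizes the exploratory microbiota endpoints on both the ITT and the Evaluable Populations.

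**The concern.** A limit of one missed dose has a purpose only if it applies to every patient who is not specifically exempted. The sentence repeats the relative clause on both sides of *or*, which makes two alternative ways to qualify. Anyone whose treatment was never suspended then meets the first alternative, and the missed-dose limit never comes into play. Conversely, a suspended patient meets the second alternative if no more than one dose was missed.

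The probable intent is that neither event occurred. One programmer could code that intent and another the literal text, and they would build different populations. The exclusion list is drawn up from this wording, and a change of rule after unblinding would be hard to defend.

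A second, smaller matter is the four-day condition for patients who progress to infection. Someone taken off treatment before Day 4 dosing is complete cannot meet it on a plain reading, while someone who progresses later can. Membership therefore depends partly on the timing of a post-randomization outcome.

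**Working it through.** **Inputs.** Section 2.2.1 gives the frequency and duration ("inert placebo given twice daily for 7 days by intravesical catheter"). Section 2.2.3 gives 13 doses in total, with a single dose on Day 7. Section 3.2.3 gives the split into Days 1-4 and Days 5-7.

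**Reproducing the plan's dose count.** 2 × 6 + 1 = 13, which agrees with section 2.2.3. Days 1-4 hold 2 × 4 = 8 doses; Days 5-7 hold 2 + 2 + 1 = 5.

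**Applying the rule to non-progressors.** Let S mean suspended and m be the number of doses missed on Days 5-7 (0 to 5), with all 8 doses on Days 1-4 received. Doses received = 13 − m. The literal rule is *not S or m ≤ 1*; the alternative is *not S and m ≤ 1*.

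| Suspended | m | Doses received | Literal *or* | *and* |
|---|---|---|---|---|
| No | 0 | 13 (100%) | in | in |
| No | 1 | 12 (92.3%) | in | in |
| No | 2 | 11 (84.6%) | in | out |
| No | 3 | 10 (76.9%) | in | out |
| No | 4 | 9 (69.2%) | in | out |
| No | 5 | 8 (61.5%) | in | out |
| Yes | 0 | 13 (100%) | in | out |
| Yes | 1 | 12 (92.3%) | in | out |
| Yes | 2 to 5 | 11 to 8 | out | out |

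There are 2 × 6 = 12 combinations, and the two rules differ in 6 of them. The minimum for a non-progressor is 8/13 = 61.5% under *or* and 12/13 = 92.3% under *and*.

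**Progressors.** The separate sentence admits them once Days 1-4 are dosed per protocol. A patient who stops after the last Day 4 dose enters with 8/13 = 61.5% whichever operator is used. One who stops after Day 1, 2 or 3 has had 2, 4 or 6 doses (15.4%, 30.8%, 46.2% of 13) and is excluded.

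**Scale of one patient.** Section 2.2.4 gives 36 patients at 2:1. If the split is exactly 24 and 12, one misclassified patient is 1/24 = 4.2% of the active arm or 1/12 = 8.3% of placebo. The SAP gives no basis for estimating how many patients would be affected.

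**The case against.** The strongest reply is that little depends on this set. ITT is primary for the same exploratory endpoints and keeps every dosed patient (sections 3.2.2 and 3.6). Recurrence and incidence of infection are summarized on the PD Population (section 3.5), which has no four-day dosing requirement. No hypothesis is tested (section 3.1.5). The list is settled blind, so a misreading cannot be steered by treatment assignment. All of this stands and limits the weight of the point. It does not make the wording correct: blind finalization prevents selection by arm but does not repair the rule being applied.

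It is also fair to say that the extreme case is remote. It needs a patient fully dosed on Days 1-4 who misses all five remaining doses, is not regarded as suspended, does not progress and completes the study. Treatment is normally given in clinic or hospital, and section 2.2.3 expects missed doses typically to be made up. The protocol, not available here, may also define suspension in a way that catches such a patient. The intermediate cases, with two or three missed doses, are less far-fetched.

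On progressors, the reply largely succeeds. Four days of dosing is a minimum-exposure condition that applies to everyone in the set. Requiring it is a legitimate design choice when ITT is reported alongside.

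**Conclusion.** The point holds for the operator. As written, section 3.2.3 lets a non-progressor qualify with 8 of 13 doses (61.5%), where joining the conditions with *and* would require 12 of 13 (92.3%). It also admits a suspended patient with at most one missed dose. This rests on the literal reading of the sentence, and on taking per-protocol dosing on Days 1-4 to mean that all 8 doses were given.

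Three stronger readings might be inferred and are not supported:

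- That the set would contain patients with very little exposure. The Days 1-4 condition puts a floor of 8 doses under every member.
- That the *and* wording would guarantee 12 of 13 doses throughout. It does so only for non-progressors, since progressors may enter with 8 by explicit design.
- That dropping early progressors is an error to be cured by including all of them. Doing so would bring in patients with as few as one or two doses, in a set meant to reflect adequate dosing. That is a trade-off and is not required. Nor are all who progress on Days 1-4 lost: a patient who progresses on Day 4 after the last dose that day stays in.

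The impact is limited to supportive descriptive output, chiefly the exploratory microbiota summaries of section 3.6, plus the baseline table that section 3.3.4 produces for each population. No primary, safety, PK or PD result is affected. The change is worth making because it is so cheap.

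**What to change.** In SAP section 3.2.3, replace *or who have not missed* with *and who have not missed*, before the list of exclusions is finalized. Leave the sentence on progressors as it stands.

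Add one sentence, in the SAP or where the Evaluable results are reported. It should note that patients discontinued for infection before Day 4 dosing is complete fall outside the set, that membership therefore depends partly on the timing of an outcome, and that the Evaluable summaries are to be read beside ITT.

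The cost is a short wording change and possibly a slightly smaller Evaluable Population. It alters only analysis-set membership and touches no dosing or stopping rule.

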### 3.2.4 *PK Population*

The PK Population is defined as all patients who receive at least one dose of LBP-EC01 and have at least one measurable post-dose concentration of LBP-EC01. The PK Population will be the population for all PK analysis.

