#### 3.4.3 *Pharmacokinetic Concentration*

LBP-EC01 concentrations will be determined in both blood and urine by using a plaque forming assay and expressed in units of plaque forming units (PFU)/mL.

Actual sampling times that are outside the sampling time windows may be excluded from concentration summary and mean concentration plotting but will still be used in the calculations of PK parameters and individual concentration plotting.

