##### Urine

Individual urine concentrations of LBP-EC01 will be summarized by treatment at each nominal time point for the PK Population descriptively. Individual urine concentrations will also be listed for the PK Population.

Individual urine concentration will be plotted by treatment against actual sampling time points relative to dosing time. Mean ( $\pm$ SD) concentration will be plotted against nominal time points by treatment, when available.

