**Blood and Urine PK Parameters:**

Parameters	Description
$C_{\max, \text{Dose 1}}$	Maximum concentration; determined directly from the concentration time profile; if the maximum concentration occurs at more than one time point, $C_{\max}$ is defined as the first maximum value
$T_{\max, \text{Dose 1}}$	Time to $C_{\max}$ of the first dose; determined directly from the concentration-time profile
$AUC_{0-t}$	Area under the concentration vs time curve (AUC) from predose (time 0) to the last quantifiable concentration ( $C_{\text{last}}$ ) for Dose 1
$C_{\text{trough,max}}$	Minimum measured concentration from Day 1 (only including predose #2) through Day 7
$C_{\max, \text{all}}$	Max post-dose concentration determined from Day 1 through Day 7
$AI_{\text{trough}}$	Accumulation index using $C_{\text{trough}}$ (predose Day 7 / $C_{\text{trough,max}}$ )

The actual collection times will be used for the calculation of PK parameters. The Linear-Log Trapezoidal method (equivalent to the Linear Up/Log Down option in WinNonlin) will be used in the computation of all AUC values.

Additional PK parameters may be determined as appropriate.

The blood and urine PK parameters will be listed and summarized by treatment using descriptive statistics for the PK Population.

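### The trough parameter, the accumulation index and later nominal-time PK summaries are derived without asking whether the preceding dose was given

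*SAP*

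**What the plan says.** SAP 2.3.1 places PK in the primary endpoints ("as well as the PK parameters of LBP-EC01", in urine and blood). It names Cmax, Tmax and AUC0-t for blood and adds: "Other PK variables may be calculated as appropriate for the observed data".

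The PK Population in 3.2.4 is "all patients who receive at least one dose of LBP-EC01 and have at least one measurable post-dose concentration of LBP-EC01", and "The PK Population will be the population for all PK analysis". It carries no condition on dosing.

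The table in 3.4.4 ties Cmax, Tmax and AUC0-t to Dose 1. It defines the trough parameter as "Minimum measured concentration from Day 1 (only including predose #2) through Day 7" and the accumulation index AI_trough as predose Day 7 divided by that parameter.

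Section 3.4.3 says for urine, with matching wording for blood: "Individual urine concentrations of LBP-EC01 will be summarized by treatment at each nominal time point for the PK Population descriptively". Samples outside their time windows "may be excluded from concentration summary and mean concentration plotting but will still be used in the calculations of PK parameters".

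Section 3.4.2 treats a value as valid for the means if it is quantifiable and not missing. In parameters, BLQ values between or after measurable concentrations are dropped. In summaries, BLQ counts as zero.

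The SAP expects departures from dosing. Section 2.2.3 covers missed doses and says they should typically still be given. Section 3.2.3 covers suspension and discontinuation, and requires of the Evaluable Population patients "who have not missed more than one dose of study drug during the remainder of treatment". That population is not used for PK.

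**The concern.** A trough describes repeated dosing only if the dose before it was given. Otherwise it measures time off drug. The SAP sets rules for BLQ values, missing times and sampling windows, but none that looks at dosing history. A pre-dose sample drawn on schedule after a missed dose lies inside its window, so even the optional exclusion in 3.4.3 does not reach it.

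Actual collection times, which 3.4.4 prescribes, put an AUC on the right time axis. They cannot correct a minimum or a ratio of two troughs. A minimum is especially exposed, because a single washout sample determines it.

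The outputs at stake are the trough parameter, AI_trough and the later nominal-time summaries. In those summaries a patient off drug who has fallen to BLQ enters as zero. The error in AI_trough can run in either direction, depending on which dose was missed.

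**Working it through.** **Inputs from the SAP.** AM dose at 8 AM ± 2 h, PM dose 12 h ± 3 h after the AM dose, and a total of 6 × 2 + 1 = 13 doses (2.2.3). There are 36 patients at 2:1, so 36 × 2/3 = 24 active (2.2.4). The SAP states no half-life and no figure for the index, so there is nothing to reproduce.

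**Time since dose at an overnight trough.**
- PM dose given, shortest: AM at 10:00, PM 15 h later at 01:00, next AM at 06:00, which is 5 h.
- PM dose given, longest: AM at 06:00, PM 9 h later at 15:00, next AM at 10:00, which is 19 h.
- PM dose missed: 10:00 to 06:00 is 20 h, and 06:00 to 10:00 is 28 h.

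Pre-dose samples may be drawn up to 30 minutes before dosing (3.4.1), so the lower ends become 4.5 h and 19.5 h. The ranges 4.5–19 h and 19.5–28 h still do not overlap.

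**Assumed model.** Equal doses every 12 h, first-order decline with half-life h, and a quantifiable trough before every dose. Let r = 2^(−12/h). The trough before dose k+1 is T(k+1) = r × (T(k) + d(k)), with T(1) = 0 and d(k) = 1 if dose k was given, else 0. As 3.4.4 defines it, AI = T(13) / min(T(2), …, T(13)).

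Example with h = 4 h, so r = 0.125:
- All doses given: the minimum is T(2) = 0.125 and T(13) ≈ 0.125/0.875 = 0.1429. AI = 0.1429/0.125 = 1.14.
- Dose 8 (Day 4 PM) missed: T(9) = 0.125 × 0.1429 = 0.0179 becomes the minimum, and T(13) has recovered to 0.1428. AI = 8.0.
- Dose 12 (Day 6 PM) missed: T(13) = 0.125 × 0.1429 = 0.0179 is itself the minimum. AI = 1.0.

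| Assumed half-life | All 13 doses | Dose 2 missed | Dose 8 missed | Dose 12 missed |
|---|---|---|---|---|
| 2 h | 1.02 | 65 | 64 | 1.0 |
| 4 h | 1.14 | 9.1 | 8.0 | 1.0 |
| 6 h | 1.33 | 5.3 | 4.0 | 1.0 |
| 12 h | 2.00 | 4.0 | 1.95 | 1.0 |
| 24 h | 3.36 | 4.7 | 3.11 | 2.36 |

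With dose 8 missed, the reported minimum is 1.6%, 14%, 33%, 99% and 100% of its fully dosed value at 2, 4, 6, 12 and 24 h. If treatment stops after dose 6 and a Day 7 sample is still taken, AI is 1.0 at every half-life.

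**Dependence on sampling.** If troughs are taken only before doses 2, 3, 5, 9 and 13 (an assumed sparse schedule) and dose 6 is missed, AI stays at 1.02, 1.14 and 1.33 for 2, 4 and 6 h. The inflation needs a sample before the next dose.

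**Effect on the group.** Suppose all 24 active patients have an index and one of them missed dose 8. At 2, 4 and 6 h that patient's AI is inflated by 64/1.02 = 63, 8.0/1.14 = 7.0 and 4.0/1.33 = 3.0. The geometric mean rises by the 24th root of each: 1.19, 1.08 and 1.05. The arithmetic mean becomes (64 + 23 × 1.02)/24 = 3.64, (8.0 + 23 × 1.14)/24 = 1.43 and (4.0 + 23 × 1.33)/24 = 1.44.

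**The case against.** The case on the other side is substantial.

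- **Primary endpoint.** A reader might infer that the primary PK results are compromised. The SAP does not support that. The three parameters named in 2.3.1 are tied to Dose 1 in 3.4.4, and later missed doses cannot touch them. The trough and the index are primary only through the general wording on PK parameters or on other PK variables. The study tests no hypothesis. This stands.
- **Denominator.** The inflated index arises because 3.4.4 uses a minimum as the denominator, which is a separate weakness. With predose #2 as the denominator, a missed dose could only lower the index. This stands for the inflation. It does not help with a missed Day 6 PM dose, which distorts the numerator whatever the denominator.
- **Half-life.** A reader might infer that any missed dose creates false accumulation. With dose 8 missed there is none at 12 h (1.95 against 2.00) or 24 h (3.11 against 3.36). Only an early miss, such as dose 2, inflates the index there.
- **BLQ and matrix.** Deep washout that falls to BLQ is dropped from the parameters, so a false trough needs a quantifiable sample. Section 3.4 warns of little or no quantifiable drug in blood, so urine is the main matrix. In the summaries, a mean is given only if at least half the patients have quantifiable values, which limits the effect of zeros.
- **Schedule and frequency.** Sampling times are in Table 2 of the protocol, on which this check does not draw. The SAP itself confirms only predose #2 and predose Day 7. Missed doses are typically to be given late, and the SAP does not say that PK sampling continues after discontinuation. All this lowers the expected frequency. It supplies no rule for when the case occurs.
- **Spread within the windows.** Permitted overnight intervals already vary by 19 − 5 = 14 h. That is a reason to list time since last dose. It does not justify pooling dosed and undosed troughs.
- **Visibility.** Dosing and concentrations are listed, and individual plots use actual time relative to dosing. A careful reader could spot an affected patient, but the summary tables would still contain the value.

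**Conclusion.** The point holds, within limits. Followed literally, 3.4.2 to 3.4.4 put washout samples into the trough parameter, AI_trough and the later nominal-time summaries whenever a dose is missed and a quantifiable sample follows.

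The best-supported case is a missed Day 6 PM dose, because 3.4.4 itself uses the predose Day 7 sample. The index then drops to 1.0 for assumed half-lives up to 12 h. At 12 h this hides a fully dosed value of 2.00. At 2 h there is little to hide (1.02). A mid-week miss followed by a sample works the other way: 64, 8 and 4 for dose 8 missed at half-lives of 2, 4 and 6 h, with no inflation at 12 h or longer.

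These sizes rest on assumed half-lives, first-order decline and a trough before each dose. Phage replication in the bladder would change the sizes but not the mechanism. How often doses will be missed cannot be told from the SAP.

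A reader might also infer that the PK Population is wrongly defined. It need not change, because the fault lies in how samples are used and not in which patients are included. The change is worth making before database lock and unblinding, so that no exclusion is decided after the results are seen.

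**What to change.** In SAP 3.4.2 to 3.4.4:

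1. Flag and list each pre-dose concentration whose immediately preceding scheduled dose was not given, and every concentration taken during suspension or after permanent discontinuation of treatment.
2. Exclude flagged values from the trough parameter, AI_trough and the nominal-time summaries. If predose Day 7 is flagged, do not calculate AI_trough for that patient.
3. Limit the retention of out-of-window samples in 3.4.3 to AUC, Cmax and Tmax.
4. List time since last dose beside each trough, so that doses given late are visible too.

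In the model above, excluding the trough after a missed dose 8 returns AI to about 1.02, 1.14 and 1.33 at half-lives of 2, 4 and 6 h.

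The cost is a few sentences and one derived flag from the administration data that 3.3.8 already lists. No patient leaves the PK Population. The downside is a slightly smaller n for late troughs. The minimum-based denominator of AI_trough is a separate matter that this change does not settle.
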